11.3 Required Reporting: Mayo Clinic to the Masonic Cancer Center

Serious events: Beginning with the first dose of decitabine and continue through day 45 of the last treatment course, as an affiliate, Mayo will report all events meeting the definition of serious, regardless of attribution or expectedness, within 24 hours of knowledge of the event. After day 45 of the last treatment course, the investigator must report upon knowledge any event that is serious, unexpected and felt to be at least possibly related to study therapy.

Reports are to be submitted to the Study Coordinator at the University of Minnesota Masonic Cancer Center (MCC) using the SAE reporting form found in OnCore. The MCC Study Coordinator will facilitate reporting to the University Of Minnesota IRB and the FDA as required.

Stopping rule events: Any grade 4 or 5 non-hematologic, non-infectious toxicity occurring through day 45 of the last treatment course will count toward the early study stopping rule per section 13 and must be reported to the MCC Study Coordinator using the Early Stopping Rule Report Form found OnCore under the reports tab.

No more than one excess toxicity event will be accumulated per patient within in the same episode of toxicity (i.e. a grade 4 event worsening to a grade 5 is a single event) or when multiple events occur concurrently.

Events that count toward an early stopping rule do not necessarily constitute a serious adverse event requiring expedited reporting and

should be reported as such only if they meet the criteria for expedited reporting as defined in section 11.1.

Lot release issues: Any safety issues associated with the final lot release at the treating institution must be reported immediately to either [name] or [name] at the University of Minnesota (contact information on page 2) with follow-up reporting to MCC Study Coordinator using the Deviation Report found in OnCore.

Affiliate institutions will be responsible for submitting reportable events to their institutional IRB and any other required local regulatory entities.

11.4 Masonic Cancer Center Required Reporting: FDA, IRB, Miltenyi, and MCC’s SAE Coordinator

The reporting period for this study is from initiation of any study treatment through day 45 of the last treatment course; however after day 45, the investigator must report upon knowledge any study treatment related event meeting the expedited reporting criteria below.

Agency	Criteria for reporting	Timeframe	Form to Use	Submission address/ fax numbers	Copy to:
U of MN IRB	Unanticipated death of a locally enrolled subject(s); New or increased risk; Any adverse event that require a change to the protocol or consent form – refer to the IRB website for complete details	5 Business Days	IRB’s Report Form	[contact] With copy to the Mayo Clinic PI or designee	MCC SAE Coordinator MMC 6 [contact]
FDA	Unexpected and fatal or life threatening suspected adverse reaction	As soon as possible but no later than 7 Calendar-Day	UMCC SAE form	Submit as an amendment to IND With copy to the Mayo Clinic PI or designee	
	1) Serious and unexpected suspected adverse reaction or 2) increased occurrence of serious suspected adverse reactions over that listed in the protocol or investigator brochure or 3) findings from other sources (other studies, animal or in vitro testing) 4) positive HAMA in association with a grade 4 infusion reaction	As soon as possible but no later than 15 Calendar-Day			
Note: Events due to the disease under treatment or an underlying medical condition will not require reporting to the FDA for the purposes of this study					
Miltenyi	Any safety issues associated with cell processing failure or device malfunction	Refer to section 11.5			Not applicable
Masonic Cancer Center SAE Coordinator	Any event that counts toward a study stopping rule (see section 13)	Upon reporting	Study stopping rule form	SAE Coordinator [contact]	Not applicable

In each IND safety report, the sponsor must identify all IND safety reports previously submitted to the FDA concerning a similar suspected adverse reaction and must analyze the significance of the suspected adverse reaction in light of the previous, similar reports.

The SAE Coordinator will provide the Cancer Center's Data and Safety Monitoring Council (DSMC) with the SAE in an appropriate format depending on the individual SAE (as reported or in a summary format).

11.5 Reporting of Device/Processing Malfunction

Any clinically significant safety issues associated with cell processing failure or device malfunction regarding the CliniMACS® system must be reported to immediately to either [name] or [name] at the University of Minnesota (contact information on page 2) with follow-up reporting (copy U of MN study coordinator on any correspondence) to:

Miltenyi Biotec, Inc.
Attn: Regulatory Affairs
[name]
[name]
[name]

There is no specific reporting form, and at a minimum a deviation report must be completed in OnCore.

12.0 Study Data Collection and Monitoring

12.1 Data Management

This study will report clinical data using The Online Enterprise Research Management Environment (OnCore™), a web based Oracle® database utilizing study specific electronic case report forms. Key study personnel are trained on the use of OnCore and will comply with protocol specific instructions embedded within the OnCore forms. Patient demographics, patient specific study treatment calendars, targeted adverse events, reporting of deaths, and other information required for IND annual reporting will be placed in OnCore and other research databases maintained by MCC IT.

12.2 Case Report Forms

Participant data will be collected using protocol specific electronic case report forms (e-CRFs) developed within OnCore based on its library of standardized forms. The e-CRF will be approved by the study's Principal Investigator and the Biostatistician prior to release for use. The Study Coordinator or designee will be responsible for registering the patient into OnCore at time of study entry, completing e-CRFs based on the patient

specific calendar, and updating the patient record until patient death or end of required study participation.

12.3 Data and Safety Monitoring Plan (DSMP)

The study's Data and Safety Monitoring Plan will be in compliance with the University of Minnesota Masonic Cancer Center's Data & Safety Monitoring Plan (DSMP), which can be accessed at <http://www.cancer.umn.edu/exfiles/research/dandsmplan.pdf>.

For the purposes of data and safety monitoring, this study is classified as high risk (under a locally held IND). Therefore the following requirements will be fulfilled:

- The PI ([name]) will complete and submit a quarterly Trial Progress Report to the Masonic Cancer Center Data and Safety Monitoring Council (DSMC) with the understanding the Cancer Protocol Review Committee (CPRC) may require more frequent reporting.
- The PI will comply with at least twice yearly monitoring of the project by the Masonic Cancer Center monitoring services.
- The PI will oversee the submission of all reportable events per the definition of reportable in section 11.4 to the Masonic Cancer Center's SAE Coordinator, the University of Minnesota IRB, and the FDA.

In addition, at the time of the continuing review with the University of Minnesota IRB, a copy of the report with any attachments will be submitted to the Cancer Protocol Review Committee (CPRC).

IND Annual Reports

In accordance with regulation 21 CFR § 312.33, the IND sponsor ([name]) will submit a progress report annually. The report will be submitted within 60 days of the anniversary date that the IND went into effect.

12.4 Monitoring

The PI with the CTO has oversight responsibility for trial monitoring at affiliate sites. Affiliate sites must self-monitor following the University of Minnesota Masonic Cancer Center Data and Safety Monitoring Plan (DSMP - <http://www.cancer.umn.edu/exfiles/research/dandsmplan.pdf>) and the CTO Affiliate and Satellite Site Monitoring SOPs.

The investigator will permit study-related monitoring, audits, and inspections by the study's Principal Investigator and/or IND sponsor and/or any designees, the local IRB, government regulatory bodies, and University of Minnesota compliance groups. The investigator will make available all study related documents (e.g. source documents, regulatory documents, data collection instruments, study data, etc.). The investigator will ensure the capability for inspections of applicable study-related

facilities (e.g. pharmacy, diagnostic laboratory, etc.) will be available for trial related monitoring, audits, or regulatory inspections.

12.5 Record Retention

The investigator will retain study records including source data, copies of case report forms, consent forms, HIPAA authorizations, and all study correspondence in a secured facility for at least 6 years after the study file is closed with the IRB and FDA.

In addition, the Clinical Trials Office (CTO) will keep a master log of all patients participating in the study with sufficient information to allow retrieval of the medical records for that patient. Please contact the CTO before destroying any study related records.

13.0 Statistical Considerations

13.1 Simon's Two-Stage Design and Sample Size

This is a single clinic Simon's optimum two-stage phase II clinical trial designed to determine the objective response rate (CR+PR+HI) after two courses of Decitabine and Vorinostat with haploidentical NK cells in patients with high risk MDS. The null hypothesis of the study is $P_{R0} \leq 0.30$ and alternative hypothesis is $P_{R1} \geq 0.50$. Based on this design and the assumption that the majority of patients will complete both cycles of therapy, a maximum of 46 evaluable patients will be used which is sufficient to maintain an overall type I error 5% while providing 80% statistical power.

In the first stage 15 patients will be enrolled, the trial will be terminated if 5 or fewer respond. If 6 patients respond, then the trial goes on to the second stage, and 31 more patients will be studied. If the total number responding is less than or equal to 18, then this approach will be deemed unworthy of further study.

Considering a predicted dropout rate of 10% during the two courses of therapy, in order to have 15 or 46 patients evaluable for the response rate, we will need a maximum of 17 patients (if the study is stopped by 1st stage) or 51 patients (if the study proceeds to 2nd stage).

Only patients completing both course 1 and 2 of planned therapy will be evaluable for response. However, all the patients with complete or partial treatment will be included in the evaluation for toxicities.

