3.0 Study Design

This is a Phase II therapeutic trial combining Decitabine days 1-5 with oral Vorinostat twice daily days 6-15 followed by a single infusion of CD3-/CD19-enriched donor NK cells on day 17 and a short course of Interleukin-2 (IL-2) to facilitate NK cell survival and expansion. Two courses of treatment will be given separated by 6 - 8 weeks. Clinical response will be formally assessed 4 - 6 weeks after the 2nd course based on International Working Group (IWG) criteria;

however, a bone marrow evaluation will be done if the patient is taken off treatment prior to study completion. **The intent is to administer all treatment in the outpatient setting.**

The trial will use Simon's two-stage design. Fifteen patients will be enrolled in stage 1. If 6 or more of the patients achieve an objective clinical response (CR + PR + hematologic improvement (HI)), stage 2 will be activated and an additional 31 patients enrolled for a total of 46 evaluable patients. Considering a predicted dropout rate of 10% during the two courses of therapy, stage 1 will need a maximum of 17 patients or a maximum of 51 patients if the study proceeds to 2nd stage.

Research and related correlative studies will be done at baseline, between courses 1 and 2, and after completion of course 2 as per section 8.1.2.

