6.2 Patients Who Do Not Begin Study Treatment

If a patient is registered on study, and is later found not able to begin the preparative regimen (beginning with the first dose of decitabine), for whatever reason, the patient will be removed from study and treated at the physician’s discretion. The patient will be considered a screen/baseline failure and the reason for removal from study will be clearly indicated in OnCore as detailed in the study’s Affiliate Manual. The patient will be replaced.

If a patient begins treatment, and then is discontinued for whatever reason, the patient will be replaced as the clinical response (CR + PR + HI) is not evaluable for response. If the patient discontinues therapy due to toxicity, it will count towards the toxicity stopping rules. The patient must be followed for any unresolved toxicity per section 7.10.

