7.5 IL-2 (begin day 17)

Start subcutaneous IL-2 approximately 2 hours, but no earlier than 2 hours, after the NK cell infusion in the absence of grade 4 infusion related toxicity.

If the patient has experienced grade 4 infusion related toxicity and it resolves to grade 2 or better, the IL-2 may be started up to 48 hours after the NK infusion. If no IL-2 is given, the patient will be replaced for statistical analysis.

IL-2 administration: IL-2 will be given at 6 million units on days 17, 19 and 22. For patients weighing less than 45 kilograms, the IL-2 will be given at a dose of 3 million units/m² on days 17, 19 and 22. For the purposes of outpatient scheduling and/or possible delay in treatment start, dosing may be altered to avoid weekends as long as IL-2 is not given on consecutive days and completed within a week.

Pre-medication with acetaminophen 650 mg PO and diphenhydramine 25 mg PO/IV before and 4 hours after each dose of IL-2 is recommended.

Monitoring during IL-2 administration: Patients are monitored for IL-2 related toxicities on a daily basis in clinic until the day after the final IL-2 administration with increased monitoring as clinically required.

IL-2 dose-adjustment for individual patient intolerance: Fevers, rash and flu-like symptoms are expected and should be treated supportively with acetaminophen and diphenhydramine as described above. If a patient cannot tolerate full dose IL-2 due to fevers, rash or constitutional symptoms, a dose decrease to 4 million units is allowed (2 million units/m² if < 45 kg). If the patient cannot tolerate the reduced dose, the IL-2 must be permanently discontinued.

IL-2 dosing guidelines for non-hematologic grade 3-4 toxicity (CTCAE v4):

Non-hematologic grade 3 toxicity persisting for > 24 hours: Hold IL-2. If the toxicity resolves to grade 2 or better within 48 hours, the IL-2 can be resumed at a reduced dose (4 million units or 2 million units/m² if < 45 kg). If the same toxicity persists, worsens or recurs, the IL-2 must be permanently discontinued. Missed doses are not made up.

Non-hematologic grade 4 toxicity: Permanently discontinue IL-2

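### Sections 3.0 and 13.1 give 17 and 51 as maximum enrolment, but at the plan's own 10% dropout these are roughly expected numbers, and replacement under 6.2 and 7.5 has no limit

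*Combined protocol and SAP*

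**What the plan says.** Section 13.1 sets a Simon two-stage design with 15 evaluable patients in stage 1 and 46 in total. The enrolment figures are then derived: "Considering a predicted dropout rate of 10% during the two courses of therapy", and "in order to have 15 or 46 patients evaluable for the response rate", the plan states that "we will need a maximum of 17 patients (if the study is stopped by 1st stage) or 51 patients" if the second stage is reached. Section 3.0 says the same: "stage 1 will need a maximum of 17 patients or a maximum of 51 patients if the study proceeds to 2nd stage".

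Evaluability is strict. Section 13.1 says: "Only patients completing both course 1 and 2 of planned therapy will be evaluable for response".

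Replacement is open-ended. Section 6.2 says: "If a patient begins treatment, and then is discontinued for whatever reason, the patient will be replaced". It also replaces registered patients who never start treatment. Section 7.5 adds: "If no IL-2 is given, the patient will be replaced for statistical analysis". No section limits the number of replacements, and none says what happens if 17 or 51 patients are enrolled and fewer than 15 or 46 are evaluable.

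**The concern.** Dividing the target by one minus the dropout rate gives the enrolment at which the target is met on average. It does not give a number that will suffice. Calling the result a maximum promises something that the calculation does not deliver, and the promise meets a replacement rule that has no limit.

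The two statements part company when the 17th or 51st patient has been enrolled and too few are evaluable. If replacement governs, more patients than the stated maximum are treated with an investigational cell product, and each brings a donor for apheresis. If the maximum governs, the trial ends below 15 or 46 evaluable patients, and the plan gives no decision boundary for that case.

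**Working it through.** **Inputs.** Dropout 10%, targets 15 and 46 evaluable, stated maxima 17 and 51, p0 = 0.30, p1 = 0.50, stop at 5 or fewer responses of 15, negative at 18 or fewer of 46 (all section 13.1). Independence of dropouts is my assumption; the plan gives only the rate.

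**1. The plan's figures.**
- 15/0.9 = 16.67, so 17.
- 46/0.9 = 51.11, so 51 to the nearest patient and 52 rounded up.
- Adding 10% instead gives 15 × 1.1 = 16.5 and 46 × 1.1 = 50.6, which round up to 17 and 51.

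So 17 and 51 reproduce as planning inflations. Expected evaluable patients are 17 × 0.9 = 15.3 and 51 × 0.9 = 45.9; the second is just below 46.

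**2. Chance that the stated maximum is not enough.** Let D be the number of dropouts, binomial with rate 0.10.
- 17 for 15: P(D ≥ 3) = 1 − [0.9^17 + 17(0.1)(0.9^16) + 136(0.1²)(0.9^15)] = 1 − (0.167 + 0.315 + 0.280) = 0.238.
- 51 for 46: P(D ≥ 6) = 0.402.

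For 51, shortfalls of exactly 1, 2 and 3 have probabilities 0.157, 0.112 and 0.069. Together that is 0.338, or 84% of all shortfalls (0.338/0.402).

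**3. Enrolment that would suffice at 10% dropout.**

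| Evaluable target | At least 90% sure | At least 95% sure |
|---|---|---|
| 15 | 18 (0.902) | 19 (0.965) |
| 46 | 54 (0.914) | 55 (0.956) |

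**4. Cost of stopping short.** With N evaluable in total, P(positive) = Σ over x = 6 to 15 of P(X1 = x | 15, p) × P(X2 ≥ 19 − x | N − 15, p). This keeps the stage 1 rule and the requirement of more than 18 responses.

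| Evaluable N | Type I error (p = 0.30) | Power (p = 0.50) |
|---|---|---|
| 46 | 0.0499 | 0.803 |
| 45 | 0.042 | 0.788 |
| 44 | 0.034 | 0.769 |
| 43 | 0.028 | 0.745 |

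The first row confirms the plan's 5% and 80%.

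**5. Sensitivity to dropout.** The rates other than 10% are assumptions, not document figures.

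| Dropout | 17 gives fewer than 15 | 51 gives fewer than 46 |
|---|---|---|
| 5% | 5.0% | 4.1% |
| 10% (plan) | 23.8% | 40.2% |
| 15% | 48.0% | 79.7% |
| 20% | 69.0% | 95.8% |

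**The case against.** The best defence is that nothing closes enrolment at 17 or 51. The sentence in 13.1 is a forecast conditional on 10% dropout, the accrual objective is stated in evaluable patients, and 6.2 and 7.5 serve that objective. Read this way, the working rule is to replace until 15 and 46 are evaluable, and stopping short never arises. This is a plausible reading, and a reader who takes 51 as a firm cap goes further than the text does. It does not rescue the figure: if replacement governs, the stated maximum is exceeded with the probabilities in step 2.

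Three further limits stand.

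- **The 40% is conditional on stage 2 opening.** P(at least 6 responses of 15) is 0.278 at a 30% response rate and 0.849 at 50%. The overall chance that 51 is reached and proves too few is therefore about 0.278 × 0.402 = 11% or 0.849 × 0.402 = 34%.
- **A missing stage 1 patient often changes nothing.** With 14 evaluable, the decision is open only if exactly 5 have responded, which has probability 0.20 at a 30% response rate and 0.12 at 50%.
- **A reader might infer that a shortfall voids the 5% and 80% claims.** Step 4 does not support that: type I error falls, and losing 1 to 3 patients costs about 1.5 to 6 points of power.

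A reader might also infer that true dropout exceeds 10%, since 4.2.2 admits patients with prior treatment failure and 7.10 lists many reasons to stop. The documents give no rate for that group, so this stays an assumption.

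**Conclusion.** The point stands as an inaccurate enrolment statement that conflicts with the replacement rules. It is not a flaw in the design. At the plan's own 10%, and assuming independent dropouts, 17 and 51 are about the average need and prove insufficient with probability 24% and, once stage 2 opens, 40%. The 15/46 design reproduces and needs no change. The practical effect is moderate: a few more patients and donors than stated, or a small loss of power with type I error still controlled. The 10% is predicted for the two courses of therapy, so registered patients who never start, whom 6.2 also replaces, come on top of these numbers if they count as enrolled.

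**What to change.** In 3.0 and 13.1, replace the maximum of 17 and 51 with text to this effect: *expected enrolment is about 17 and 52 at 10% dropout; non-evaluable patients are replaced under 6.2 and 7.5 until 15 and 46 are evaluable.*

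Add, as a planning figure and expressly not a cap, that 19 and 55 treated patients suffice with about 95% probability at 10% dropout, and that registered patients who never start are additional. Describing 19 and 55 as a ceiling would recreate the conflict, because they too are exceeded 3.5% and 4.4% of the time (1 − 0.965 and 1 − 0.956).

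The cost is a wording amendment and a slightly less favourable stated enrolment. No evaluable patients are added, and the decision boundaries do not change.

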7.6 Second Treatment Course

Any patient who failed prior treatment (i.e. met section 4.2.2 of the eligibility criteria at enrollment) will have a bone marrow biopsy and aspirate performed prior to the start of the 2nd treatment course.

A second treatment course will be given 6 to 8 weeks after the start of course 1, identical to the first course substituting the frozen NK cell product for the fresh product, unless medically unsafe.

The following criteria must be met before a new treatment course is started:

- ANC recovery to baseline documented prior to course 1
- Platelet transfusion that can be managed safely in the outpatient setting

- Treatment related non-hematologic toxicity, except fatigue, alopecia, resolved to \leq grade 2
- Absence of rapid disease progression as defined in Section 7.10

If the above requirements are not met, delay and reassess weekly until recovery occurs. If more than 2 weekly delays occur (>8 weeks from the start of course 1) without hematological recovery and/or non-hematologic treatment related toxicity resolution, the patient will be taken off study. A bone marrow biopsy will be done to assess response to the therapy up to that point or to determine etiology for inadequate recovery of counts.

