7.10 Duration of Therapy

Patients will receive two courses of study treatment unless one or more of the following occurs:

- Patient withdraws consent or is non-compliant
- Criteria in section 7.6 for a 2nd treatment course are not met
- Medically unsafe, in the opinion of the treating investigator to continue with the treatment plan and based on development of grade 4 non-hematologic toxicities

- Intercurrent illness that prevents further administration of treatment
- Unacceptable toxicity
- Evidence of rapid disease progression defined as $\geq 20\%$ peripheral blood blast percentage suggesting progression to acute leukemia

Any patient who discontinues therapy before the completion of 2 courses should have a bone marrow biopsy and aspirate performed at the time treatment is discontinued. Those who are not evaluable per section 13 will be followed only until the resolution or stabilization of treatment related toxicity. No further follow-up for this study will be required, other than recording the date and cause of death upon knowledge in OnCore.

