7.11 Follow-up

All evaluable patients will be followed for response and survival for 1 year from study enrollment unless the patient withdraws consent.

Ongoing therapy with maintenance hypomethylating agents or proceeding to allogeneic stem cell transplantation will be at the discretion of the patient's primary oncologist.

For patients completing 1 year of follow-up no further data collection will be required for this study; however the date and cause of death will be entered in OnCore upon knowledge for IND annual reporting.

An exception to this for all patients is the reporting upon knowledge of any serious, unexpected and at least possibly study treatment related event per sections 11.3 and 11.4.

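### Both Simon decisions rest on patients who completed two courses; treated patients who stop early are replaced, and no response rate in all treated patients is planned beside it

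*Combined protocol and SAP*

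**What the plan says.** Section 13.1 limits the primary analysis: "Only patients completing both course 1 and 2 of planned therapy will be evaluable for response". Two other rules remove and replace treated patients. Section 6.2 says: "If a patient begins treatment, and then is discontinued for whatever reason, the patient will be replaced". Section 7.5 adds: "If no IL-2 is given, the patient will be replaced for statistical analysis". The synopsis and sections 3.0 and 13.1 express the 15 and 46 of the Simon design as evaluable patients.

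Patients who stop early are not lost altogether. Section 13.1 says that "all the patients with complete or partial treatment will be included in the evaluation for toxicities", and section 6.2 counts a discontinuation for toxicity toward the toxicity stopping rules. When a patient cannot start course 2 because of delayed recovery, section 7.6 provides: "A bone marrow biopsy will be done to assess response to the therapy up to that point". Section 7.10 asks for a marrow at any early discontinuation.

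Follow-up differs by evaluability. Section 7.11 says: "All evaluable patients will be followed for response and survival for 1 year from study enrollment". For the others, section 7.10 says: "Those who are not evaluable per section 13 will be followed only until the resolution or stabilization of treatment related toxicity", with nothing further "other than recording the date and cause of death upon knowledge in OnCore".

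Section 13.3 gives a confidence interval method for the response probability, but no analysis of response in all treated patients.

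**The concern.** Whether a patient enters the primary denominator is decided after treatment starts, partly by events related to outcome. Appendix VI classes death during treatment and disease progression as failure. A patient who dies before finishing course 2, or stops because peripheral blasts reach 20% (the rapid progression rule in 7.10), is nevertheless replaced rather than counted as a failure. The marrow taken at discontinuation can document a response or its absence, but 13.1 gives that finding no place in the primary rate.

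The completer rate decides whether stage 2 opens and whether the regimen is judged worth pursuing. If stoppers respond less often than completers, that rate is higher than the one a patient starting decitabine could expect, and the plan reports nothing that would show the gap.

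**Working it through.** **Inputs.** From 13.1: null rate 0.30, alternative 0.50; stop if 5 or fewer of 15 respond; success needs at least 19 of 46; dropout 10%. Assumed: the response rate in stoppers, as a multiple f of the completer rate c. Dropout values other than 10% are also assumed.

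**Step 1: the plan's own figures.** With X1 ~ Bin(15, p) and X2 ~ Bin(31, p), P(success) = sum over x = 6 to 15 of P(X1 = x) × P(X2 ≥ 19 − x).
- p = 0.30: P(success) 0.0499, P(pass stage 1) 0.2784.
- p = 0.50: P(success) 0.8032, P(pass stage 1) 0.8491.

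The stated 5% and 80% are reproduced. The Simon arithmetic is sound if p is the rate in the patients who are counted, that is, completers.

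**Step 2: what the completer rate hides.** Suppose all 51 planned patients start treatment and the 5 who stop do not respond. A bare success of 19/46 = 41.3% is then 19/51 = 37.3% of treated patients. At stage 1, 6/15 = 40.0% is 6/17 = 35.3%.

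**Step 3: if 30% were an all-treated rate.** With dropout d, all-treated rate = c(1 − d) + f·c·d, so c = 0.30 / [(1 − d) + d·f]. Putting c into the step 1 rule with d = 0.10:

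| Stoppers respond at | c | Type I error | Pass stage 1 |
|---|---|---|---|
| completer rate (f = 1) | 0.30/1.00 = 0.3000 | 5.0% | 27.8% |
| half of it (f = 0.5) | 0.30/0.95 = 0.3158 | 7.8% | 32.6% |
| zero (f = 0) | 0.30/0.90 = 0.3333 | 12.0% | 38.2% |
| 1.5 times (f = 1.5) | 0.30/1.05 = 0.2857 | 3.2% | not needed |

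With f = 0, type I error is 7.8% at 5% dropout (c = 0.30/0.95) and 18.2% at 15% dropout (c = 0.30/0.85 = 0.3529).

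**Step 4: the reverse case.** If 50% is a completer rate but the same 5/15, 18/46 rule is applied to all treated patients at 10% dropout:
- no stopper responds: p = 0.50 × 0.90 = 0.450, power 61.9%, pass stage 1 73.9%;
- stoppers respond at half the completer rate: p = 0.50 × 0.95 = 0.475, power 72.1%, pass stage 1 79.9%.

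**Step 5: who is removed.** Of the six reasons for stopping in 7.10, three are toxicity or progression: medically unsafe with grade 4 toxicity, unacceptable toxicity, and rapid progression. A fourth, failing the course 2 criteria in 7.6, mixes progression and unresolved toxicity with slow count recovery. The other two are withdrawal or non-compliance, and intercurrent illness. Only death and progression are failures under Appendix VI. A patient who responds after course 1 and then withdraws is also dropped, which lowers the completer rate.

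**The case against.** The strongest reply is that this is a completer design throughout. The primary objective (1.1) and endpoint (9.0) concern response once two courses have been given. Section 13.1 ties the 5% and 80% to 46 evaluable patients and then defines evaluable as completing both courses. No passage presents 30% as an all-treated rate. That reply stands: the natural reading keeps type I error at 4.99%. A reader might infer from step 3 that the trial's false-positive rate is really 12.0%. The documents do not support this, because it needs 30% to be an all-treated rate and no stopper to respond, and they state neither.

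A reader might also infer that every early stopper is a hidden failure. That goes too far as well. Toxicity, intercurrent illness, withdrawal and slow count recovery are not failures under Appendix VI by themselves. Patients with marrow-only progression who still meet the course 2 criteria can complete and count as non-responders. Toxicity discontinuations count toward the stopping rules through 6.2.

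Finally, an all-treated set includes patients who never received NK cells, and some stoppers would be assessed while counts are expected to be low. That is a fair reason to keep the completer rate, but not to leave the all-treated rate unreported.

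**Conclusion.** The point holds as a gap in the analysis set and in reporting, not as a failed error rate. On the completer reading, the operating characteristics are as stated. What is missing is any estimate for all patients who start treatment, although some of those replaced are failures by the plan's own criteria. The completer rate probably overstates response in that population; this is a judgement from the listed reasons for stopping, since the documents give no response rate for stoppers. The bias is zero if stoppers respond as often as completers, and reversed if they respond more often.

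The range of 5.0% to 12.0% at 10% dropout applies only if 30% was meant as an all-treated rate and stoppers respond no more often than completers. Section 13.1 gives no source for 30% or 50% and never names their population outright, so this should be settled in the text. Should be fixed: the evidence does not require a redesign.

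**What to change.** 1. In 13.1, state which population the 30% and 50% describe.
2. In 13.3, pre-specify the response rate in all patients who receive the first dose of decitabine, reported beside the completer rate at both the stage 1 and the final decision. Count deaths and progressions before completion as failures. Count other early stoppers as non-responders unless an Appendix VI response is documented from data already collected (weekly blood counts, discontinuation marrow). List the number excluded from the completer set and the reasons.

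The boundaries, sample size and treatment stay as they are; the cost is wording in two sections and one extra table.

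The all-treated rate will probably be lower than the completer rate. It will also be biased somewhat downward, because some stoppers will have too little data: the calendar records transfusion history only before treatment and 4-6 weeks after course 2, and transfusion-based improvement needs an 8-week comparison.

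If the sponsor prefers to make the all-treated set primary, it should first justify 30% and 50% as all-treated rates, or recompute and restate the operating characteristics. Keeping 5/15 and 18/46 without doing so risks power of 61.9% to 72.1% (step 4) if 50% is a completer rate.
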